5.0 TREATMENT PLAN

5.1 Study Summary

Patients with advanced poor-risk clear-cell RCC who have not had any prior systemic targeted therapy will be randomized fairly in a 1:1 ratio to receive pazopanib or temsirolimus as first-line therapy. Patients will be stratified upfront by nephrectomy status (yes/no) and prior cytokine/vaccine therapy (yes/no). At the time of disease progression, patients will be offered the option of crossover to receive the agent they did not receive in the first-line.

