- Patients on temsirolimus will have serum chemistry and electrolytes including total protein, albumin, alkaline phosphatase, AST, ALT, calcium, LDH, total bilirubin, BUN, creatinine, phosphorus, glucose, sodium, potassium, chloride, and carbon dioxide will be done every 2 weeks for the first 8 weeks and every 4 weeks thereafter. Fasting lipid panel every 4 weeks for the first 8 weeks, every 8 weeks x 2, and every 16 weeks thereafter. CBC with platelet count and differential will be done every week for patients on temsirolimus.

- Record concomitant medications with each history and physical.
- Reconcile the medication diary provided during treatment with each history and physical for those on pazopanib.
- Adverse events will be assessed at each visit and monitored throughout the study.
- 12-Lead Electrocardiogram will be repeated at Cycle 2 Day 1, 12 weeks later, and every 16 weeks after that for patients on Pazopanib. (see Section 6.1.1.4 for additional details of QT interval monitoring) Patients receiving temsirolimus will have an ECG done every 16 weeks.
- Optional blood specimens for future correlative studies will be obtained every 8 weeks and at progression.
- Serum amylase and lipase will be obtained only as clinically indicated.
- Serum T4 and TSH will be obtained every 8 weeks for patients receiving pazopanib.
- Repeat radiological studies (CT, MRI as indicated) to evaluate response every 8 weeks. Studies to confirm a complete response or document progressive disease will be performed as needed. Patients who are progression free after 1 year can have their imaging studies obtained every 16 weeks.
- Echocardiogram or MUGA scan (echocardiogram preferred) will be repeated every 24 weeks and as clinically indicated.

Outside Physician Participation During Treatment (Temsirrolimus Patients may have interim infusions with local MD)

1. MDACC Physician communication with the outside physician is required prior to the patient returning to the local physician. This will be documented in the patient record
2. A letter to the local physician outlining the patient's participation in a clinical trial will request local physician agreement to supervise the patient's care (Appendix J); A copy of the protocol abstract and evaluation during treatment will be provided to the local physician with the letter.

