3. Protocol required evaluations outside MDACC will be documented by telephone, fax or e-mail. Fax and/or e-mail will be dated and signed by the MDACC physician, indicating that they have reviewed it.
4. Changes in drug dose and/or schedule must be discussed with and approved by the MDACC physician investigator, or their representative prior to initiation, and will be documented in the patient record.
5. Documentation to be provided by the local physician will include drug administration records, progress notes, reports of protocol required laboratory and diagnostic studies and documentation of any hospitalizations.
6. The home physician will be requested to report to the MDACC physician investigator all life threatening events within 24 hours of documented occurrence.
7. Patients will return to MDACC every 8 weeks for evaluation.

8. Patients on pazopanib/torisel who have reached 12 months without progression may see their local physician and will return to MDACC every 8-16 weeks for evaluation and restaging.

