13.0 STATISTICAL CONSIDERATIONS

This is a randomized, two-arm, parallel group, phase II trial enrolling advanced, poor-risk, clear-cell RCC. Patients will be fairly randomized to either temsirolimus (control arm) or pazopanib (experimental arm).

The maximum sample size to be accrued is 90 patients (45 in each treatment arm). The primary measure of efficacy and primary endpoint is progression free survival (PFS). PFS will be monitored on an interim basis and we will use stopping rules for futility to serve as guidelines for early termination. The stopping rules are ad-hoc in nature but are selected in a manner such that the overall type 1 error is controlled at a one-sided 10% with 80% power.

Descriptive and inferential statistics will be used to summarize treatment effects. The mean, standard deviation, median, 25% percentile, 75% percentile, minimum, and maximum will be reported for continuous variables. For discrete variables, descriptive analyses will be based on the distribution of discrete outcomes and will be reported as percentages and patient counts. Time to event endpoints will be descriptively summarized by Kaplan-Meier curves. Point and interval estimates of treatment effect will be based on maximum likelihood methods. For binomially distributed variables, we will report differences in proportions between treatment groups and the 95% confidence interval associated with those differences. We will estimate treatment effects for time to event variables via hazard ratios using Wald scores from Cox proportional hazard regression models. Unless stated otherwise, all statistical tests will be assessed using a two-sided $\alpha = 0.05$ alpha significance level and confidence intervals will be constructed using two-sided 95% and will be based on the normal approximation. Although multiple secondary endpoints will be evaluated we will make no adjustment for multiplicities associated with these multiple tests.

Estimation of Sample Size

The clinical hypothesis we are assessing in this trial is whether patients receiving the experimental therapy have a lower hazard of progression or death relative to patients receiving the control therapy. The statistical hypothesis is stated as:

$$H_0: \log(HR)=0$$

$$H_A: \log(HR)<0$$

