Where HR is the hazard ratio (experimental:control). For sample size calculation purposes we assume that the median PFS in the temsirolimus arm is 60% that of the pazopanib arm (3.8 months versus 6.1 months). The sample size estimate is based on a one-sided log-rank test with type one error equal to 0.10 and power of 0.80.

We will conduct an interim analysis for futility after 42 events have been observed. If the p-value used to assess futility at the interim analysis is greater than 0.4798 we will stop the trial early for futility.

Secondary Objectives

Overall survival: Overall survival is calculated from day of therapy initiation to the date of death. Patients who are lost to follow-up will be censored at date of last contact.

We will use the Kaplan-Meier estimator to estimate the OS for each group of patients (control, experimental), and the log-rank statistic will be used to test for treatment differences. We will also use the Cox proportional hazards regression model to estimate the hazard ratio (experimental:control) for OS with a 95% confidence interval.

We will also assess the response rate and report 95% confidence intervals.

Additional analyses:

Demographics

For each treatment group (control, experimental), summary statistics will be provided for age, weight, baseline disease status and prior treatments.

Toxicities

Toxicities and side effects that will be evaluated include, but are not limited to infections, renal toxicity, hepatic toxicity, and pulmonary toxicity. Methods of assessment will include monitoring blood counts, and performing laboratory tests as indicated by clinical signs and symptoms. Evidence of toxicities or adverse events will be recorded at all clinic visits. All observed toxicities and side effects will be graded (NCI CTC-AE v. 4.0) for all patients and the degree of association of each with pazopanib or temsirolimus assessed. The incidence and severity of toxicities will be compared between the two treatment arms with Fisher's exact test.

Stratification Factors

The Pocock-Simon Minimization Method will be used to randomize patients according to the following stratification factors:

- Prior nephrectomy status (yes or no)
- Prior cytokine/vaccine therapy (yes or no)

The randomization program based on this method will be developed in the Department of Biostatistics and Applied Mathematics, and the program will be available via an intranet web site of MD Anderson Cancer Center.

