15.0 DATA AND PROTOCOL MANAGEMENT

15.1 Protocol Compliance

The attending physician or designee will see each patient for evaluation of tumor response and toxicity every 8 weeks. All required interim and pretreatment data should be available, and the physician must make a designation as to tumor response and must provide a detailed description

of toxicity, when appropriate. If dose modifications or treatment interruptions are necessary, the details must be carefully documented.

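### After year 1 the tumour-assessment interval is left open in Section 5.4 and does not match Section 15.1; the possible effect on PFS is small, and one common interval removes it

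*Combined protocol and SAP*

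**What the plan says.** Section 13.0 makes PFS the primary endpoint. Section 5.4 sets imaging every 8 weeks in both arms and then adds: "Patients who are progression free after 1 year can have their imaging studies obtained every 16 weeks". Note t of the study calendar (Section 9.0) repeats this permission.

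Item 8 of the outside-physician list, also in Section 5.4, covers patients on either drug "who have reached 12 months without progression may see their local physician and will return to MDACC every 8-16 weeks for evaluation and restaging". Item 7 of the same list has patients return to the centre every 8 weeks.

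Section 15.1 says the attending physician or designee "will see each patient for evaluation of tumor response and toxicity every 8 weeks". It has no exception after 1 year.

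No passage names who picks the interval or gives a criterion. Section 13.0 has no rule for dating a PFS event and no sensitivity analysis for assessment timing. Section 15.3 has independent radiologists review all imaging.

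**The concern.** Progression is dated at the scan that shows it. A patient scanned every 16 weeks will, on average, have a later recorded progression than the same patient scanned every 8 weeks. If the two arms use different intervals, their PFS curves separate after year 1 without any drug effect.

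No blinding is described. One drug is a weekly infusion, the other is taken at home, and at progression patients are offered the agent they have not had, so assignment is known. An optional interval therefore gives room for unequal scanning. Central reading addresses how a scan is read, not when it is taken.

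At stake are the one-sided 10% type I error and the 80% power that Section 13.0 states for the PFS comparison. Separately, a site that scans at 16 weeks follows 5.4 but departs from 15.1.

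**Working it through.** **Inputs from the documents.** "The sample size estimate is based on a one-sided log-rank test with type one error equal to 0.10 and power of 0.80" (Section 13.0). The control median PFS is taken as "60% that of the pazopanib arm (3.8 months versus 6.1 months" (Section 13.0). Maximum 90 patients, 45 per arm (13.0), randomised 1:1 (5.1). Interim futility analysis at 42 events (13.0). The final event count, accrual period and follow-up are not stated.

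**Reproducing the design.** HR = 3.8/6.1 = 0.623 under exponential PFS. With z(0.10) = 1.2816 and z(0.80) = 0.8416, the squared sum is 4.508.
- Freedman: 4.508 × (1.623/0.377)² = 83.5, so 84 events. Half of 84 is the stated interim of 42.
- Schoenfeld: 4 × 4.508/(ln 0.623)² = 80.5, so 81 events.

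The stated power is reproduced: 80.2% at 81 events and 81.3% at 84 (Schoenfeld).

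**Who can be affected.** Only patients progression free at 12 months, S(12) = exp(−ln 2 × 12/median):
- temsirolimus: exp(−ln 2 × 12/3.8) = 0.112; × 45 = 5.0 patients
- pazopanib: exp(−ln 2 × 12/6.1) = 0.256; × 45 = 11.5 patients

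That is about 17 of 90. Both medians fall well before 12 months, so median PFS is unaffected. For an affected patient the recorded date moves by at most one extra 8-week step.

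**Simulation.** 40,000 trials of 45 per arm, exponential PFS, every event dated at the next scan. Scans are 8-weekly to week 56 (the first 8-weekly scan after 52 weeks), then 8- or 16-weekly, with ±1 week jitter. The test is a one-sided log-rank at 0.10. T = temsirolimus, P = pazopanib; interval in weeks after week 56.

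| Censoring | Intervals | Type I error, both medians 3.8 | Type I error, both medians 6.1 | Power, 3.8 vs 6.1 |
|---|---|---|---|---|
| None | T 8, P 8 | 10.5% | 10.5% | 81.9% |
| None | T 16, P 16 | 10.5% | 10.6% | 81.6% |
| None | T 8, P 16 | 12.0% | 13.1% | 84.3% |
| None | T 16, P 8 | 9.2% | 8.5% | 79.1% |
| Uniform 6–36 months (assumed) | T 8, P 8 | 10.4% | 10.4% | 78.6% |
| Uniform 6–36 months (assumed) | T 8, P 16 | 11.4% | 12.2% | 80.6% |
| Uniform 6–36 months (assumed) | T 16, P 8 | 9.5% | 8.8% | 76.3% |

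With no drug effect and no censoring, the mean HR at T 8, P 16 is 0.98 (medians 3.8) or 0.97 (medians 6.1). Reversed, it is 1.015 or 1.025.

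A variant with an assumed 36-month accrual and analysis at an assumed 84 events (20,000 trials) agrees:
- common 8-week interval: type I error 10.3%, power 80.5%
- common 16-week interval: 10.1–10.3%, power 80.3%
- only pazopanib moves: 11.6% (medians 3.8) to 13.1% (medians 6.1)
- only temsirolimus moves: power 77.3%
- half of pazopanib and no temsirolimus patients move: 11.0–11.4%

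With 25% use on temsirolimus and 75% on pazopanib, again at 84 events, type I error is 10.4–11.1% against 10.1–10.4% at baseline.

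**The case against.** The strongest reply is that this is a deliberate, symmetric provision. Section 5.4 speaks of patients in general and item 8 names both drugs. If both arms use the same interval, the table shows that nothing is lost.

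A reader might infer more than the documents support, in four ways.
- **Three conflicting rules.** The 16-week permission and the 8-to-16-week range are both in Section 5.4 and are compatible. The mismatch is with 15.1; item 7 states the general 8-week rule, which item 8 qualifies.
- **Unequal use is likely, because weekly infusion and home dosing give different visit rhythms.** Pazopanib patients keep 8-weekly history and physical examination, urinalysis and thyroid tests with no 1-year end. Quality-of-life assessments are 8-weekly in both arms. Temsirolimus infusions may be given locally. Visits to the centre may well be similar. Unequal use is possible, in either direction, and no more.
- **Treating physicians choose the interval.** No decision-maker is named.
- **A larger error.** Starting the change at week 48 gives 12.6–14.4%, but the permission begins only after 1 year.

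The 11–13% figure also needs complete separation between arms, and its upper end needs a control median of 6.1 months where the design assumes 3.8. Dating every event at a scheduled scan is a worst case: deaths have exact dates, and 5.4 allows extra studies to document progression. If an assumed 30% of events are dated exactly, complete separation at medians of 3.8 gives 10.8%.

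All of this reduces the size, and it stands. What it leaves is that 5.4 and 15.1 disagree, the interval is optional in an unblinded trial, and no planned analysis addresses scan timing.

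**Conclusion.** The point holds as a minor one. The interval that dates late PFS events is optional in one section and fixed in another, and the documents do not ensure that it is applied equally by arm.

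If only pazopanib patients moved to 16 weeks, type I error would be about 11–13% instead of about 10%. Partial imbalance adds about 1 point or less. If only temsirolimus patients moved, power would fall to about 77–79% where a common 8-week schedule gives 80.5–81.9%; the run with 6–36 month censoring starts lower and loses a similar amount.

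A reader might conclude that the primary result is at risk. The documents do not support that: few patients reach 1 year, median PFS does not move, and even complete separation shifts the no-effect HR by only about 2–3%.

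The figures rest on exponential PFS, every event dated at a scan, a change at week 56, and assumed accrual, censoring and final event counts.

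**What to change.** Reconcile Section 5.4 (the imaging bullet and items 7 and 8 of the outside-physician list), calendar note t and Section 15.1 to one imaging interval after year 1. It should be counted from randomisation and identical in both arms, with no per-patient option. The choice of interval is the sponsor's; either common schedule keeps the test at its own level in the simulations.

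If patients have already been scanned on mixed intervals, add a PFS sensitivity analysis that places late progressions on a common assessment grid or treats them as interval-censored.

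The cost is a wording amendment, plus a few more or fewer scans for the roughly 17 of 90 patients expected to be progression free at 1 year.

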11.0 Serious Adverse Event Reporting (SAE)

An adverse event or suspected adverse reaction is considered “serious” if, in the view of either the investigator or the sponsor, it results in any of the following outcomes:

- Death
- A life-threatening adverse drug experience – any adverse experience that places the patient, in the view of the initial reporter, at immediate risk of death from the adverse experience as it occurred. It does not include an adverse experience that, had it occurred in a more severe form, might have caused death.
- Inpatient hospitalization or prolongation of existing hospitalization, unless hospitalization is for:

- routine treatment or monitoring of the studied indication, not associated with any deterioration in condition (specify what this includes)
 - elective or pre-planned treatment for a pre-existing condition that is unrelated to the indication under study and has not worsened since the start of study drug
 - treatment on an emergency outpatient basis for an event not fulfilling any of the definitions of a SAE given above and not resulting in hospital admission
 - social reasons and respite care in the absence of any deterioration in the patient’s general condition
- A persistent or significant incapacity or substantial disruption of the ability to conduct normal life functions.
 - A congenital anomaly/birth defect.
 - Important medical events that may not result in death, be life threatening, or require hospitalization may be considered a serious adverse drug experience when, based upon appropriate medical judgment, they may jeopardize the patient or subject and may require medical or surgical intervention to prevent one of the outcomes listed in this definition. Examples of such medical events include allergic bronchospasm requiring intensive treatment in an emergency room or at home, blood dyscrasias or convulsions that do not result in inpatient hospitalization, or the development of drug dependency or drug abuse (21 CFR 312.32).

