 - Important medical events as defined above, may also be considered serious adverse events. Any important medical event can and should be reported as an SAE if deemed appropriate by the Principal Investigator. All events occurring during the conduct of a protocol and meeting the definition of a SAE must be reported to the IRB in accordance with the timeframes and procedures outlined in “The University of Texas M. D. Anderson Cancer Center Institutional Review Board (IRB) Policy for Investigators on Reporting Unanticipated Adverse Events for Drugs and Devices”. For this protocol adverse events will be captured according to the Recommended Adverse Event Recording Guideline for Phase II protocols (below).

Recommended Adverse Event Recording Guidelines					
Attribution	Grade 1	Grade 2	Grade 3	Grade 4	Grade 5
Unrelated	Phase I	Phase I	Phase I Phase II	Phase I Phase II Phase III	Phase I Phase II Phase III
Unlikely	Phase I	Phase I	Phase I Phase II	Phase I Phase II	Phase I Phase II

				Phase III	Phase III
Possible	Phase I	Phase I	Phase I	Phase I	Phase I
	Phase II	Phase II	Phase II	Phase II	Phase II
		Phase III	Phase III	Phase III	Phase III
Probable	Phase I	Phase I	Phase I	Phase I	Phase I
	Phase II	Phase II	Phase II	Phase II	Phase II
		Phase III	Phase III	Phase III	Phase III
Definitive	Phase I	Phase I	Phase I	Phase I	Phase I
	Phase II	Phase II	Phase II	Phase II	Phase II
		Phase III	Phase III	Phase III	Phase III

The Investigator or physician designee is responsible for verifying and providing source documentation for all adverse events and assigning the attribution for each event for all subjects enrolled on the trial

- **Serious adverse events will be captured from the time of the first protocol-specific intervention, until 30 days after the last study treatment/intervention, unless the participant withdraws consent. Serious adverse events must be followed until clinical recovery is complete and laboratory tests have returned to baseline, progression of the event has stabilized, or there has been acceptable resolution of the event.**
- **Additionally, any serious adverse events that occur after the 30 day time period that are related to the study treatment must be reported in accordance with the IRB policy. This may include the development of a secondary malignancy.**

Reporting to FDA:

- SAE's will be reported per regulatory (local and federal) guidelines.

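### Local physicians are asked to report only life-threatening events within 24 hours, so other serious events at a local site have no reporting deadline

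*Combined protocol and SAP*

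**What the plan says.** The list headed Outside Physician Participation During Treatment, in Section 5.4, governs patients seen away from the study centre.

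- **Prompt reporting (item 6).** "The home physician will be requested to report to the MDACC physician investigator all life threatening events within 24 hours of documented occurrence". This is the only item with a time limit on what the local physician tells the centre about an event.
- **Documentation (items 3 and 5).** Evaluations done outside are passed on by telephone, fax or e-mail, and a centre physician signs what arrives by fax or e-mail. The local physician also supplies infusion records, clinic notes, required test results and paperwork on any admission. No deadline is given.
- **Dose or schedule changes (item 4).** These need the centre's agreement beforehand.
- **Centre visits (items 7 and 8).** "Patients will return to MDACC every 8 weeks for evaluation". After 12 months without progression, patients on either drug may be followed locally and return every 8 to 16 weeks.
- **What the local physician receives (item 2).** "A copy of the protocol abstract and evaluation during treatment will be provided to the local physician with the letter".

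Section 11 sets a wider test for seriousness. Besides death, life-threatening events and congenital anomaly, it includes "Inpatient hospitalization or prolongation of existing hospitalization" (with listed exceptions), "A persistent or significant incapacity or substantial disruption of the ability to conduct normal life functions", and important medical events by judgement. It then states: "All events occurring during the conduct of a protocol and meeting the definition of a SAE must be reported to the IRB".

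**The concern.** The study team must report every event that meets Section 11, but it can report only what it has heard about. For patients treated locally, the one rule that produces prompt news covers a single Section 11 category. That category is drawn tightly: Section 11 confines it to immediate risk of death from the event as it happened, and excludes events that would have been fatal only in a worse form. An admission for infection, lung infiltrates or falling renal function can be serious under Section 11 and still fall outside item 6. Section 3.2.5 names such risks for temsirolimus, some with fatal cases.

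At stake are how soon the investigator responsible for attribution and for agreeing dose changes knows of a serious event, and whether reports to the IRB are timely.

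**Working it through.** The plan gives no figure to reproduce. The check sets the provisions side by side and then works out how long the gap can be.

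**1. Which serious categories have a prompt route from the local site?**

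| Section 11 category | In item 6 (24 hours)? | Other route in 5.4 | Deadline on that route |
|---|---|---|---|
| Life-threatening | Yes | Items 3, 5 | None |
| Death | Not named | Items 3, 5 | None |
| Hospitalization | No | Item 5, by name | None |
| Incapacity | No | Items 3, 5 (clinic notes) | None |
| Congenital anomaly | No | Items 3, 5 (clinic notes) | None |
| Important medical event | No | Items 3, 5 (clinic notes) | None |

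**2. Does another rule supply the missing deadline?**

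- Item 4 brings contact only if the local physician decides to change dose or schedule. If infusions continue, it is not triggered.
- Section 11's 24-hour company reporting runs from learning of the event and stands under a heading for patients taking pazopanib. The five-working-day limit for deaths is in the same part. Neither puts a duty on the local physician.
- Section 11 makes the investigator or a designee responsible for verifying and attributing events, which presupposes that the centre has been told.

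So there is a route, but no deadline.

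**3. How long until the next centre visit?**

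Inputs: intervals of 8 weeks (item 7) and up to 16 weeks (item 8); windows of ±7 days (Section 5.4) and ±3 days (Section 9.0). If one visit is early and the next late, the longest gap is interval + 2 × window.

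| Schedule | Nominal | With ±3 days | With ±7 days |
|---|---|---|---|
| 8 weeks | 56 days | 56 + 6 = 62 | 56 + 14 = 70 |
| 16 weeks | 112 days | 112 + 6 = 118 | 112 + 14 = 126 |

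Eight weeks is therefore the nominal interval, not an upper limit.

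**4. Who is exposed?**

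Before 12 months, local infusion is offered to temsirolimus patients. That means the control arm in first line and pazopanib-arm patients after crossover (Sections 5.1 and 5.6). After 12 months item 8 covers both drugs. If PFS is exponential with the design medians in Section 13, the share progression-free at 12 months is 2^(−12/median):

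- temsirolimus: 2^(−12/3.8) = 0.112, or 5.0 of 45;
- pazopanib: 2^(−12/6.1) = 0.256, or 11.5 of 45.

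On those assumptions the longest interval would be open to more pazopanib than temsirolimus patients. The plan does not say how many patients will be treated locally.

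**The case against.** The strongest reply is that item 6 is an extra, expedited request to a physician outside the study team and takes nothing away from Section 11. Temsirolimus patients have weekly blood counts and a history and physical every 4 weeks. Adverse events are assessed at each visit, and evaluations done locally go to the centre under item 3. Item 5 names hospitalizations outright. The Appendix J letter is not in the supplied text and may ask for more. All of this stands. It shows that the documents do not contradict each other and that a channel exists, but it supplies no deadline.

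Three stronger readings are tempting, and the documents do not support them.

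- *Serious events would go unseen.* Items 3 to 5 provide a route, and an event can still be recorded at the next centre visit. Late is supported; missed is not.
- *Seven local doses would follow an unreported event.* Weekly dosing does put 8 − 1 = 7 infusions between 8-weekly visits. But Section 6.1.2.2 holds temsirolimus for reactions of grade 3 or above and for low counts. For an event meeting those criteria, seven uninterrupted doses would mean that the hold was not applied.
- *Serious toxicity would be understated in the control arm.* Before 12 months pazopanib patients have a history and physical only every 8 weeks, fortnightly blood tests only for the first 8 weeks, and no local physician asked to report. Crossover puts pazopanib-arm patients under item 6 too. The Fisher comparison in Section 13 can still count an event recorded late. The direction of any bias is not established.

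**Conclusion.** The point holds as one of reporting timeliness and safety oversight. Item 6 is narrower than the seriousness definition the investigator must report against, and nothing else in the supplied text sets a deadline for the remaining categories. Followed as written, the plan allows a non-life-threatening serious event at a local site to reach the investigator only at the next centre visit: nominally 56 days, at most 70 on the 8-week schedule and 126 on the 16-week schedule.

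These are longest-case delays. They assume that the local paperwork does not arrive sooner and that the unseen letter adds no deadline. The number of patients affected is unknown. No effect on the primary analysis follows, and no between-arm bias is claimed. This is a cheap improvement rather than an error that undermines the trial.

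**What to change.** In Section 5.4:

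1. **Item 6:** replace the reference to life-threatening events with *all events meeting the serious definition in Section 11, including deaths and hospitalizations*, and run the 24 hours from the local physician becoming aware.
2. **Item 5:** add a deadline for sending hospitalization records; its length is for the sponsor to set.
3. **Item 8:** state that both duties apply to patients followed locally after 12 months.
4. **Item 2:** add Section 11 and the existing Section 6 text to what is sent, and keep the Appendix J letter consistent.

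The ±7-day and ±3-day windows in Sections 5.4 and 9.0 should be reconciled as well, though the fix does not depend on which is kept.

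The cost is a protocol and letter wording change and a few more calls or faxes from local physicians. It needs no extra visits or tests and leaves every dosing and hold rule as it is.
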